## **DATA ANALYSIS**

Reactivity variables (craving, latency to smoke, and smoke intake) will be entered into 3 (Study drug: NRT, VAR, PLAC) x 2 (Environment: smoking, nonsmoking) x 2(Time) repeated measures ANOVAs with random-effects. We hypothesize that personal smoking, as compared to nonsmoking environments, will be associated with greater reactivity (i.e. increased craving and smoke intake; decreased latency to smoke). A Medication x Environment X Time interaction will be characterized by decreased reactivity to smoking as compared to nonsmoking environments in the VAR and NRT groups as compared to the PLAC group.

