**Cue-Reactivity sessions.** In the week following the study drug induction phase there will be 2 cue-reactivity sessions, which will be at least 24 hours apart but less than 72 hours apart. The first cue-reactivity session will take place 8 days (+ 2 day window) after the randomization visit. Both 1 hour cue-reactivity sessions will begin following 6 hours smoking abstinence. Participants will provide breath and saliva samples. To verify smoking abstinence, the breath CO level must be less than 60% of the highest CO measurement obtained from either the screening session or training session. Subjective and behavioral responses will be assessed in two separate laboratory sessions—one involving reactivity to personal smoking environment cues; the other reactivity to personal nonsmoking environment cues (order randomly assigned and counterbalanced). Following CO assessment, participants will be seated in front of a computer monitor. Participants will be video recorded using a handheld recorder during the session to gather data about their smoking behavior. They will be instructed that throughout the session pictures of places will appear on the screen and they are to focus intently on the environment they see in front of them. The cue-reactivity (CR) sessions will be computer automated: participants will 1) complete on-screen assessments of craving and mood 2) view personal smoking or nonsmoking environment cues, and 3) complete assessments a 2nd time. Following completion of the 2nd assessment, participants will be instructed to watch the slides and concentrate on their content, followed immediately by a screen stating that “At any time from this point on, you may smoke as much as you like until the end of the session. You do not have to smoke if you choose not to.” The environment cues will then be presented for the next 12 minutes. During this ad lib smoking period, choice to smoke, latency to first puff and other smoking topography will be collected while the participant focuses on the picture cues. Following the ad lib period, a prompt to complete assessments will again appear. During the task, heart rate and respiration will be measured using a BIOPAC system.

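### The planned Drug x Environment x Time model does not fit latency or smoke intake, which occur once per session, and latency has no rule for sessions without a puff

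*Combined protocol and SAP*

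**What the plan says.** The DATA ANALYSIS section gives one model form for three outcomes: "Reactivity variables (craving, latency to smoke, and smoke intake) will be entered into 3 (Study drug: NRT, VAR, PLAC", crossed with Environment and then "x 2(Time) repeated measures ANOVAs with random-effects". The drug hypothesis follows: "A Medication x Environment X Time interaction will be characterized by decreased reactivity to smoking". The rest of that sentence compares smoking with nonsmoking environments in the two active groups against placebo. No outcome is exempted from the Time factor, and its two levels are not defined.

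The Cue-Reactivity sessions paragraph (DESIGN AND PROCEDURES) sets out the measurements. There are two sessions per participant, one per environment. Within a session, participants first "complete on-screen assessments of craving and mood", then view the cues, then "complete assessments a 2nd time". After the ad lib period they are prompted to complete the assessments a third time.

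In the ad lib period itself, "choice to smoke, latency to first puff and other smoking topography will be collected". Participants are told "You do not have to smoke if you choose not to", and the window is fixed: "The environment cues will then be presented for the next 12 minutes". No section says how latency is scored or analysed when there is no puff. Smoke intake is not defined further.

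**The concern.** Two things do not fit together.

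- **Time factor.** A repeated-measures factor needs at least two values per participant and environment. Latency and smoke intake appear to have one. The interaction that carries the drug hypothesis would then not exist for two of the three named reactivity outcomes. For craving it exists, but which two of three assessments define it is open. The third follows optional smoking, so the choice matters.
- **Sessions without a puff.** Not smoking is an allowed response. Latency is then known only to exceed 12 minutes, and an ordinary ANOVA has no value to enter. A random effect for participant does not solve this, because the absence of a puff is itself the response. Dropping such sessions would condition on a choice made after randomisation, which the drugs may alter. Scoring them as 12 gives a valid 12-minute restricted mean, but a different estimand. The plan does not choose.

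**Working it through.** **No plan figure to reproduce.** The documents give 3 x 40 = 120 completers but no alpha, power, effect size, SD or smoking rate. Steps 1 to 3 need no further assumption. Steps 4 and 5 are conditional.

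**1. What can be estimated.** Inputs: 40 per arm (Randomization and Medication); one session per environment and one ad lib period per session (Cue-Reactivity sessions).

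- Model parameters: 3 x 2 x 2 = 12.
- Craving with two Time levels: 120 x 2 x 2 = 480 values, 12 cells filled, design rank 12.
- Latency or intake: 120 x 2 = 240 values, 3 x 2 = 6 cells filled, design rank 6.
- Not estimable: Time (1), Drug x Time (2), Environment x Time (1) and the three-way term (2), which makes 1 + 2 + 1 + 2 = 6.

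**2. Could Time mean first versus second session?** Code environment E, session T and order group O as +1 or -1. Each person sees each environment once, so T = E x O. Hence E x T = O, and Drug x E x T = Drug x O. The matrix has full rank, but the three-way term has become a between-person order contrast, not the stated hypothesis.

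**3. Craving.** Three assessments per session (before cues, after cues, after ad lib) stand against two unnamed Time levels.

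**4. What dropping no-puff sessions would do to latency.** Assume exponential latency with mean m, and a drug that doubles the mean.

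- No-puff share: p = exp(-12/m)
- 12-minute restricted mean (no puff = 12): m(1 - p)
- Mean among sessions with a puff: m - 12p/(1 - p)

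| Means (min) | No puff | Restricted means | Difference | Puff-only difference | Share kept |
|---|---|---|---|---|---|
| 4 vs 8 | 5% vs 22% | 3.80 vs 6.21 | 2.41 | 1.18 | 49% |
| 6 vs 12 | 13.5% vs 36.8% | 5.19 vs 7.59 | 2.40 | 0.89 | 37% |
| 8 vs 16 | 22% vs 47% | 6.21 vs 8.44 | 2.23 | 0.70 | 32% |
| 10 vs 20 | 30% vs 55% | 6.99 vs 9.02 | 2.04 | 0.58 | 28% |

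**5. Power for Drug x Environment, one active arm against placebo.** Assumptions: 40 per arm, two-sided 0.05, gamma frailty with variance 0.5, and placebo nonsmoking-session hazard h per minute. Sessions are either kept (no puff = 12) or dropped. With this frailty the no-puff share at hazard h is (1 + 6h)^-2.

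- *Drug fully abolishes cue reactivity* (cue HR 2.5, drug HR 0.5, interaction HR 0.4; 2.5 x 0.4 = 1). Both drug-arm sessions have hazard 0.5h. No-puff share: (1 + 0.75)^-2 = 33% at h = 1/4, and (1 + 0.375)^-2 = 53% at h = 1/8. Power is about 0.55-0.62 keeping all sessions and 0.17-0.31 dropping them. Separate runs differ by about 2 points.
- *Drug halves reactivity on the log scale* (drug HR 0.7; cue 2.5 with interaction 0.63, or cue 2.0 with interaction 0.71; same h). Power is 0.10-0.21 keeping and 0.08-0.13 dropping, a gap of about 1 to 10 points.
- *Nearly everyone smokes* (h = 1, HRs as in the first case). Drug-arm no-puff share: (1 + 3)^-2 = 6%. Power is 0.25 keeping and 0.29 dropping, so keeping brings no gain.

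**The case against.** **The Time problem is loose drafting.** The plan's first hypothesis, an environment effect with a direction for each outcome, needs no Time factor. The verbal description of the drug hypothesis is already the Drug x Environment contrast. Remove the factor that cannot apply and one drug interaction remains. This stands. A reader might infer that the drug hypothesis is untestable for latency and intake, or that the drug test is wholly open to choice after the data are seen. The documents do not support that. The model as written is still wrong for these outcomes and should say what it means.

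**Smoke intake is undefined.** Topography over 12 minutes could be split into time bins, which would supply a Time factor. That is true, but no section plans it, and latency to first puff cannot be binned. For intake, the finding rests on the measurement as described.

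**Nobody said that no-puff sessions are dropped.** A reader might infer it from the word ANOVA, but the text does not say so. Choice to smoke is recorded, so these sessions are observed, and intake has a natural value of zero. This stands. The gap is a missing rule, mainly for latency.

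**The power figures can be made to look alarming.** The large gap needs full abolition of cue reactivity and a third to a half of drug-arm sessions without a puff. Participants smoke at least 5 cigarettes a day, have abstained for 6 hours and may smoke freely. The documents neither support nor exclude such rates. This also stands, so a large expected power loss cannot be claimed.

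**Conclusion.** The point holds, and it should be fixed.

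- **Without further assumptions:** the stated three-way model cannot be estimated for latency, nor for smoke intake as described (rank 6 of 12). Reading Time as session order does not restore the stated hypothesis. Drug x Environment is the testable drug term and matches the plan's own verbal description. The Time levels for craving are ambiguous; its analysis is otherwise unaffected.
- **Also without further assumptions:** latency is right-censored at 12 minutes when there is no puff, and the planned ANOVA gives neither a censoring nor a scoring rule.
- **Conditional on assumed smoking rates and on sessions being dropped:** 28-49% of the within-window latency difference would remain. The power penalty is large only under full abolition with many no-puff sessions, about 1 to 10 points under half-abolition, and about nil if nearly everyone smokes. These figures show what the missing rule could cost. They do not forecast what it will cost.

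**What to change.** Amend the DATA ANALYSIS section as follows.

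1. Keep the Time factor for craving only and name its two levels, for example before and after cue viewing.
2. Analyse latency with Drug, Environment and Drug x Environment, without Time, keeping every session. Name one method in advance: time to first puff censored at 12 minutes, with a subject frailty or subject-clustered variance; or 12-minute restricted mean latency (no puff = 12) in a mixed model.
3. Define smoke intake and analyse it with the same terms, scoring sessions without a puff as zero.
4. State the drug hypothesis for latency and intake as the Drug x Environment interaction.

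A model for choice to smoke is optional, because it is not a named reactivity outcome.

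**Cost:** wording only, since the data are already collected. A hazard ratio needs a proportional-hazards check. A restricted mean says nothing beyond 12 minutes. Intake with zeros is skewed and may need a suitable model. Neither latency method is better throughout: in the full-abolition case, a clustered Cox model gave power 0.63 and 0.50 at h = 1/4 and 1/8, against 0.53 and 0.61 for the restricted mean in the same runs. Naming one in advance therefore matters more than which one is named.

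### For latency and smoke intake, the model leaves out the breath CO and craving measured before the cues in each session, so the Drug x Environment test may lose some precision (no bias)

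*Combined protocol and SAP*

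**What the plan says.** The Data Analysis section is the whole analysis plan. It states that "Reactivity variables (craving, latency to smoke, and smoke intake) will be entered into 3 (Study drug: NRT, VAR, PLAC"). The other two factors are Environment and Time, each with two levels, and the method is a repeated measures ANOVA that includes random effects. It lists no covariate and no session-order term, and no other section adds one.

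Design and Procedures, under Cue-Reactivity sessions, describes what each session collects:

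- **Before the cues.** Abstinence is required: "Both 1 hour cue-reactivity sessions will begin following 6 hours smoking abstinence". Breath CO checks it: "the breath CO level must be less than 60% of the highest CO measurement obtained from either the screening session or training session". No other use of that CO value is stated. Participants then "complete on-screen assessments of craving and mood 2) view personal smoking or nonsmoking environment cues, and 3) complete assessments a 2nd time".
- **After the second rating.** There is a 12-minute period in which smoking is allowed but optional: "During this ad lib smoking period, choice to smoke, latency to first puff and other smoking topography will be collected".
- **Allocation of environments.** Each person has one smoking-environment and one nonsmoking-environment session, 24 to 72 hours apart, with "order randomly assigned and counterbalanced".

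**The concern.** Craving is rated before and after the cues, so its own starting level enters through Time. Latency and smoke intake have one value per session and no starting value, so Time does nothing for them.

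The abstinence rule limits deprivation differences but does not equalise them. The CO rule is an upper limit only, and any level of pre-cue craving is accepted. A person can therefore arrive more deprived on one day than on the other, and this plausibly affects how soon and how much they smoke. Each environment has its own session, so such a difference goes into the smoking-minus-nonsmoking contrast as noise.

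What is at stake is precision in the Drug x Environment test for two of the three reactivity outcomes. The plan gives no power calculation for that test.

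**Working it through.** **Plan's own figures.** The documents give no alpha, power, effect size, SD or within-person correlation, so there is no power figure to reproduce. The sample size is consistent: 3 x 40 = 120.

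**Inputs.** 40 per arm comes from Randomization and Medication. Assumed: two-sided alpha of 0.05, base power of 50% or 80%, and r between 0.2 and 0.5.

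**Step 1: reduce the test.** With one value per session, Drug x Environment is a one-way comparison of three arms on

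D = (smoking-session value) - (nonsmoking-session value).

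It has 2 and 120 - 3 = 117 degrees of freedom. Stable differences between people cancel in D; session-level differences do not.

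**Step 2: add the covariate.** Let W be the same session difference in the pre-cue value, and r the within-arm correlation of D and W (the multiple correlation if CO and craving both enter). Then

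Var(D | W) = (1 - r²) Var(D),

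and the noncentrality is divided by (1 - r²). The equivalent unadjusted sample size per arm is 40 / (1 - r²).

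**Step 3: put in the numbers.** With 117 df, noncentrality 9.886 gives 80% power and 5.085 gives 50%. At r = 0.3, for example, 9.886 / 0.91 = 10.86, which gives 83.8%.

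| r (assumed) | Error variance removed | Power from 80% | Power from 50% | Equivalent n per arm |
|---|---|---|---|---|
| 0.2 | 4% | 81.7% | 51.7% | 41.7 |
| 0.3 | 9% | 83.8% | 54.1% | 44.0 |
| 0.4 | 16% | 86.8% | 57.6% | 47.6 |
| 0.5 | 25% | 90.4% | 62.9% | 53.3 |

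The table uses one covariate (116 df). With two deviations plus order (114 df), the powers change by less than 0.1 point. The gain reaches 5 points only at r of about 0.35 or more.

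**Step 4: check validity.** In simulation with no interaction, the adjusted and unadjusted tests both rejected close to 5% of the time. This included a case where both active arms shift the covariate equally in both sessions: that shift cancels in W. When the covariates were unrelated to the outcome, adjustment cost up to about 1 point of power.

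**Step 5: allow for people who do not smoke.** Latency is cut off at 12 minutes. With about 60% not smoking (an assumption), simulated gains for latency fell to about 1 to 2 points at an underlying r of 0.3, and to about 4 to 7 at 0.5, depending on the assumed effect.

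**The case against.** The strongest reply is that this is a preference and not a defect. The design already works on deprivation: a fixed abstinence period, a CO check at both sessions, a short interval, each person as their own control, and randomised order. The unadjusted test is valid. All of that stands, and it limits the point to an optional gain.

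The reply is also right about size. The relevant r is between two difference scores, and nothing in the documents shows that it reaches 0.35. That the CO rule permits very different arrival values is not evidence that they occur. Optional smoking and the 12-minute limit reduce the gain further.

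A third objection is carry-over. Craving before session 2 follows session 1's cues and smoking by 24 to 72 hours, so its session difference could hold some drug-by-environment signal. This cannot be excluded in principle, but a simulated moderate drug-specific carry-over into session-2 craving did not inflate the error rate. Randomised order and the unadjusted analysis give further protection.

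A reader might go further and infer that the comparison is biased, or that a loss of 10 points or more is to be expected. The documents support neither. Order is randomised and both values precede that session's cues, so the omission does not bias the contrast; and the larger figures need an r that the documents do not give.

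**Conclusion.** The point holds as a possible loss of precision in the Drug x Environment test for latency and smoke intake. It does not affect the validity of the planned test, and for craving the pre-cue value already enters through Time. Under a linear model the gain forgone is about 2 to 4 power points at r of 0.2 to 0.3 and about 10 to 13 at r = 0.5, and less if many participants do not smoke. All values of r are assumptions.

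The conclusion also assumes that smoke intake is scored from the ad lib smoking topography. The Data Analysis section does not define it. If it were a rise in CO, the starting CO would already enter through the outcome, but no CO reading after smoking is described. The change is a low-cost improvement and not a necessary correction.

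**What to change.** In the Data Analysis section, for latency and smoke intake only:

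1. Add two session-level covariates, pre-cue breath CO and pre-cue craving, each as the session value minus the participant's own two-session mean. Add session order.
2. Do not add the participant means. They are measured on study drug and are not needed for Drug x Environment. The deviations sum to zero within each person, so on their own they leave the drug main effect intact.
3. Prespecify this adjusted model as the primary test of Drug x Environment for these two outcomes, and report the unadjusted model as a sensitivity analysis. Naming the primary in advance avoids a choice between two p-values.

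The same edit should state that Time has no second level for these outcomes, since the covariates belong in a Drug x Environment model.

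The cost is a few sentences and no new data. Each added term uses one degree of freedom (117 to 114 for all three), and up to about 1 point of power is lost if the covariates turn out to be unrelated to the outcome.

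### The order of smoking and nonsmoking cue sessions is randomised, but the model has no first/second-session term, so any session shift stays in the error for latency and smoke intake

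*Combined protocol and SAP*

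**What the plan says.** Under DESIGN AND PROCEDURES, Cue-Reactivity sessions, each participant attends two sessions, "which will be at least 24 hours apart but less than 72 hours apart". The sessions differ in content: "one involving reactivity to personal smoking environment cues; the other reactivity to personal nonsmoking environment cues (order randomly assigned and counterbalanced").

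Within a session, participants "complete on-screen assessments of craving and mood 2) view personal smoking or nonsmoking environment cues, and 3) complete assessments a 2nd time". The ad lib smoking period comes next. They are told "You do not have to smoke if you choose not to", and "The environment cues will then be presented for the next 12 minutes". In that period "choice to smoke, latency to first puff and other smoking topography will be collected while the participant focuses on the picture cues". Then "Following the ad lib period, a prompt to complete assessments will again appear". Craving is therefore rated three times per session, while latency and smoke intake each have one value per session.

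The DATA ANALYSIS section enters craving, latency and smoke intake alike into "3 (Study drug: NRT, VAR, PLAC) x 2 (Environment: smoking, nonsmoking) x 2(Time) repeated measures ANOVAs with random-effects". The drug hypothesis is a Medication x Environment x Time interaction; a main hypothesis about Environment is also stated. Time is not defined, and no session, period or order term appears anywhere.

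**The concern.** The design randomises which environment comes first, but the analysis does not use that information. If responses drift between the first and second session (familiarity with the procedure, a nearer quit day, changing drug levels), the drift is added to the smoking-minus-nonsmoking difference of participants who see smoking cues second and subtracted from that of participants who see them first. Balanced order cancels this in the average but not in the spread.

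For latency and smoke intake this matters most. With one value per session there is no before/after pair, so the drug question can be tested only as Drug x Environment, and that is where a constant session shift sits. For craving, a constant shift cancels in the three-way test, and only a shift that differs between the two ratings (Session x Time) would matter.

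What is at stake is precision. The Cue-Reactivity sessions text also does not say whether order is balanced within each drug arm.

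**Working it through.** **Meaning of Time.** Two readings are possible.

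- *Before/after cues.* This fits the stated hypothesis and exists for craving, although the plan does not say which two of the three ratings are used. It cannot apply to latency or smoke intake. The model then has no session term.
- *First/second session.* A session term would then be present and the concern would fall. But each person would fill only two of the four Environment x Time cells, and the three-way interaction would compare order groups between people, which is not the stated hypothesis.

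The rest uses the first reading.

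**Inputs.** From the documents: 40 per arm, three arms, 120 in all (3 x 40); two sessions, one environment each. The documents give no alpha, power, effect size, SD or session shift, so there is no planned figure to reproduce. Assumed: two-sided 0.05; shifts s of 0.3, 0.5 and 0.7 SD of the smoking-minus-nonsmoking difference; and the effects that 80% power would need with no shift:

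- one drug against PLAC: (1.960 + 0.842) x √(2/40) = 0.63 SD
- Environment, 120 people: (1.960 + 0.842) x √(1/120) = 0.26 SD

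**Mechanism.** For each person let D = smoking minus nonsmoking value. The person's own level cancels in D, so a random intercept has nothing to absorb. Then D = drug-arm mean + s·o + e, with o = +1 if the smoking session is second, −1 if first, and e of SD 1. With balanced order and o left out, the error variance is 1 + s².

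- s = 0.3: 1.09, so 40 per arm acts like 40/1.09 = 37
- s = 0.5: 1.25, like 32
- s = 0.7: 1.49, like 27

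These effective sizes apply when order is balanced only overall. If order is 20:20 within each arm, the drug contrast itself carries no shift, but its standard error is still computed from 1 + s². The test is then conservative: size is about 2Φ(−1.960·√(1+s²)) and power about Φ(2.802 − 1.960·√(1+s²)). At s = 0.5, √1.25 = 1.118, so size is 2Φ(−2.191) = 0.028 and power Φ(0.610) = 0.73.

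**Simulation, one drug against PLAC, normal outcome** (40,000 runs):

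| Shift (SD) | No term, balanced within arm: power (size) | No term, balanced overall only: power (size) | With session term: power |
|---|---|---|---|
| 0 | 0.79 | 0.79 | 0.79–0.80 |
| 0.3 | 0.77 (0.041) | 0.76 (0.05) | 0.79–0.80 |
| 0.5 | 0.72 (0.028) | 0.70 (0.05) | 0.79–0.80 |
| 0.7 | 0.65 (0.018) | 0.62 (0.05) | 0.79–0.80 |

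A shift of 0.1 SD leaves power at 0.79.

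**Other tests, same shifts.**

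- Three-arm 2-df Drug x Environment test, both drugs at 0.63 SD, balanced within arm: 0.83 falls to 0.79, 0.74, 0.65; with the term, 0.82 to 0.83.
- Environment: 0.80 falls to 0.78, 0.74, 0.67; with the term, 0.81.
- Outcomes with a limit (no smoking recorded as 12 minutes or zero intake), balanced within arm. With 20% of session values at the limit: 0.74 falls to 0.71, 0.66, 0.58, against 0.74, 0.73, 0.72 with the term. With 40%: 0.65 falls to 0.62, 0.57, 0.50, against 0.64, 0.63, 0.61. The term recovers most of the session loss, not the loss from the limit.
- Craving three-way test: a constant shift of 0.7 or even 1.4 SD costs nothing (0.79 to 0.80). A Session x Time shift gives 0.77, 0.72, 0.65 within arm; adding that term restores 0.79 to 0.80.

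**Balance within arm.** If order is fixed only at 60:60 overall, a given arm splits 24:16 or worse with probability 0.175 (hypergeometric: 120 people, 60 with smoking second, 40 in the arm). A 24:16 split in one arm against 16:24 in another moves their contrast by 0.2s − (−0.2s) = 0.4s.

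**Shift in one arm only.** With a 0.7 SD shift in one of the two arms and order balanced within arm, power is about 0.71 without a session term, 0.75 with it, and 0.79 with Drug x Session as well.

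**The case against.** The strongest reply has four parts.

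1. *The documented defect is that Time is undefined; the missing session term is inferred from one reading.* This is partly right. The only two-level Time that latency and intake could support is session, and on that reading the term exists. But the three-way interaction would then test something other than the stated hypothesis, so the text needs correcting either way.

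2. *The drug test the plan names is the three-way interaction, which a constant shift leaves untouched.* This is true for craving. For latency and smoke intake that test cannot be fitted, and Drug x Environment is what remains. The Environment hypothesis, which the plan does state, is also exposed.

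3. *There is no validity problem and no evidence of a shift.* This stands. Counterbalancing protects against order bias, and type I error is at or below 0.05. The sessions are close together, both after 6 hours' abstinence and both after induction. All shift sizes are assumed, and the loss becomes material only at about 0.5 SD. The schedule does leave room for a shift: the first session is set 8 days (+2) after randomization, close to the capsule change scheduled for Days 8–14, and the second is nearer the quit attempt. That is plausibility, not evidence.

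4. *Full recovery assumes the same shift in every arm.* This also stands. With a shift in one arm only, the common term recovers about half of the loss.

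**Conclusion.** The concern holds as a gain in precision at almost no cost. It is not a bias and not a missed power target, since the plan states none. On the only reading of Time that fits the stated hypothesis, a session shift stays in the error of the Environment and Drug x Environment tests for latency and smoke intake.

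The size depends on assumed values. Power for one drug against PLAC is 0.77, 0.72 or 0.65 instead of about 0.79 for shifts of 0.3, 0.5 or 0.7 SD of the difference, with order balanced within arm, and nothing visible is lost at 0.1 SD. Recovery to 0.79–0.80 assumes a normal outcome and a shift common to all arms. For craving, only a Session x Time effect would cost anything. The change should be made; confidence in its practical benefit is moderate because the documents do not show that a shift exists.

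**What to change.** In DATA ANALYSIS:

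- Define Time for each outcome. For craving, say which two of the three ratings are used. For latency and smoke intake, drop the Time factor.
- Latency and smoke intake: fit Drug x Environment with session number (first/second) as a within-person fixed effect. Keep the term if latency is analysed as a censored time.
- Craving: add Session and Session x Time.
- State whether environment order is balanced within each drug arm.
- Add Drug x Session as a sensitivity analysis, in case the shift differs by drug.

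Gender and smoking-frequency strata could also be added as fixed effects. This is minor: they help only the between-person drug main effect, for which no hypothesis is stated.

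The cost is wording, one degree of freedom for latency and smoke intake, and two for craving, before any sensitivity analysis. No new data are needed, because session order is already set by the randomisation. With no shift, adding the term leaves power unchanged to within simulation error (0.790 against 0.790 with order balanced within arm; 0.793 against 0.798 balanced overall).
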